pressure control) and time. Time (in days) will be treated as a continuous variable with values ranging from 1 (first day of enrollment) to 272 (final day of enrollment) and will be analyzed using restricted cubic splines with multiple knots to allow for non-linearity resulting from seasonality or secular trends. In addition to assessing for an overall group effect within the model, we will estimate the differences between each pair of modes by extracting 95% confidence intervals from the model.

Sensitivity Analyses of the Primary Clinical Outcomes:

We will repeat the primary clinical outcome analysis with adjustment for pre-specified baseline covariates.

We will repeat the analyses of the primary outcome and feasibility outcomes among all patients enrolled in the trial including those initiated on invasive mechanical ventilation in the study ICU during one of the pre-specified 3-day washout periods.

Analysis of Effect Modification for the Primary Outcomes.

We will examine whether pre-specified baseline variables modify the effect of study group on the primary clinical outcome using formal tests of statistical interaction in a proportional odds model. Independent variables will include study group assignment, the potential effect modifier of interest, and the interaction between the two (e.g., study group * history of COPD) and time. Significance will be determined by the P value for the interaction term, with values less than 0.10 considered to suggest a potential interaction and values less than 0.05 considered to confirm an interaction.

We will examine whether the following baseline variables modify the effect of study group on the primary outcome:

- Age (continuous variable);
- Duration of invasive mechanical ventilation prior to enrollment (0 minutes; 1 to 360 minutes; >360 minutes);
- Pre-enrollment fraction of inspired oxygen (FiO₂)(continuous variable);
- SOFA score at enrollment (continuous variable);
- Shock receiving vasopressors (yes, no)
- Indication for intubation (categories are not mutually exclusive)
 - Hypoxemic respiratory failure (yes, no);
 - Hypercarbic respiratory failure (yes, no);
 - Altered mental status or airway protection (yes, no);
- Chronic Obstructive Pulmonary Disease (yes, no);

Analysis of the Exploratory, Feasibility, and Clinical Outcomes

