Each of the exploratory outcomes will be compared between groups in an intention-to-treat fashion in the primary analysis population. Continuous outcomes will be compared between groups in a similar manner as the primary clinical outcome. A logistic model will be used for binary outcomes, a multinomial model for categorical outcomes, and a proportional odds model for ordinal and continuous outcomes.

Corrections for multiple testing

We have pre-specified a single primary clinical outcome, which will have a test of statistical significance for difference between groups. Consistent with recommendations of the Food and Drug Administration and the European Medicines Association, the clinical outcome will be tested using a two-sided p-value with a significance level of 0.05. For all other analyses, emphasis will be placed on the estimate of effect size with 95% confidence intervals, as recommended by the International Committee of Medical Journal Editors, and no corrections for multiple comparisons will be performed.

Handling of missing data

The primary outcome is not anticipated to be missing for any patients. Missing data will not be imputed for the primary outcome or any secondary or exploratory outcomes. In adjusted analyses, missing data for covariates will be imputed using multiple imputations.

Interim Analysis

In addition to ongoing monitoring of safety throughout the trial, we will plan for the DSMB to conduct a single interim analysis for safety after the ICU has been assigned to each of the three study modes, that is, after enrollment of patients for 3 months. At the interim analysis, the DSMB will evaluate the incidence of the following outcomes across the study groups (volume control, pressure control, or adaptive pressure control):

- Pneumomediastinum or pneumothorax during the course of mechanical ventilation,
- Episodes of hypoxemia while receiving invasive mechanical ventilation: SpO₂ < 85% for more than 5 minutes,
- In-hospital mortality to study day 28.

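### Nine uncorrected interaction tests are each allowed to 'confirm' an effect modifier at P<0.05; if no interaction is real, the chance of at least one false confirmation is roughly 28–37%

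*Combined protocol and SAP*

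**What the plan says.** The document is the combined protocol and SAP; all the relevant text is in Section 10.0.

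- **Analysis of Effect Modification.** Each modifier is entered in a proportional odds model with study group, time and the group-by-modifier interaction. Every interaction is then judged on its own P value alone, by this rule: "values less than 0.10 considered to suggest a potential interaction and values less than 0.05 considered to confirm an interaction".
- **The modifiers.** Age, duration of ventilation before enrollment (three categories), pre-enrollment FiO2, SOFA score, shock on vasopressors, three indications for intubation, and COPD. The indications may overlap and each is coded yes/no, so they are three variables. That makes nine tests.
- **Corrections for multiple testing.** Only the primary clinical outcome is given a significance test at 0.05. For all other analyses, "emphasis will be placed on the estimate of effect size with 95% confidence intervals", and the plan states that it makes no correction for multiple comparisons.
- **Sample size justification.** The trial length was set for feasibility. The stated 80% power is for a 3-day between-group difference in ventilator-free days. No power is given for any interaction.
- **Interim Analysis.** For three safety outcomes, the plan does divide 0.05 by 3.

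**The concern.** The plan attaches its strongest label to some of its least protected tests. An interaction P value of 0.04, one of nine examined and uncorrected, would have to be reported as confirmed if the rule were followed literally. The rule looks only at the P value; the size of the interaction and the width of its interval play no part.

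The multiplicity subsection makes no correction and instead emphasises estimation for non-primary analyses. That is a reasonable position while those analyses are read as estimates. The confirmation rule weakens it for these nine tests.

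At stake is what the report may say about which patients respond differently to a ventilator mode. The primary test, the sample size and the conduct of the trial are untouched.

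**Working it through.** **Inputs from Section 10.0:** nine modifiers; thresholds 0.05 and 0.10 per test; no correction; 202 patients per group; SD 11 days; two-sided alpha 0.05; stated power 80% for 3 days.

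**Step 1: the plan's own figure.** The plan gives no error rate for the interaction tests, so the only figure to reproduce is the power statement.
- Standard error of a difference between two modes: 11 × √(2/202) = 1.0945 days.
- Power for 3 days: Φ(3/1.0945 − 1.96) = 78.3%, within 2 points of the stated 80%.
- Difference detectable with 80% power: (1.960 + 0.842) × 1.0945 = 3.07 days.

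This uses no design effect for the monthly blocks. It serves here only to show what the power statement covers.

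**Step 2: what that implies for an interaction.** Assume a yes/no modifier split evenly, so 101 patients per cell. The standard error of the difference of differences is 11 × √(4/101) = 2.189 days, twice that of the main effect. The detectable interaction is then 2 × 3.07 = 6.13 days, and larger with an uneven split. This is a linear approximation to the planned ordinal model.

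**Step 3: false confirmations with independent tests and no true interaction.** One overall P value per modifier is assumed (2 degrees of freedom, or 4 for the three-category variable), with each test holding its nominal level.
- At least one P<0.05: 1 − 0.95^9 = 0.370.
- At least one P<0.10: 1 − 0.90^9 = 0.613.
- Upper bound for P<0.05 under any dependence: 9 × 0.05 = 0.45.
- Indication counted as a single test (seven tests): 1 − 0.95^7 = 0.302.

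**Step 4: correlated modifiers.** The documents give no correlations, so these are assumptions. Simulated chance of at least one P<0.05 among nine null interaction tests:

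| Assumed correlation between modifiers | Chance |
|---|---|
| Mixed pattern (SOFA–shock 0.5, FiO2–hypoxemic failure 0.5, hypoxemic failure–altered mental status −0.5, hypercarbic failure–COPD 0.4, others small or zero) | 35% |
| Common correlation 0.3 | 33% |
| Common correlation 0.5 | 28% |
| Common correlation 0.7 | 22% |
| Common correlation 0.9 | 14% |

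The last two rows assume that all nine variables move closely together, which is hard to credit for a list running from age to COPD. They are shown as limits.

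**Step 5: a corrected threshold.** 0.05/9 = 0.0056 per test; family-wise error under independence is 1 − (1 − 0.05/9)^9 = 4.9%.

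**The case against.** The best defence is that nothing is hidden. The modifiers are pre-specified, the absence of correction is declared, and uncorrected exploratory subgroup tests are ordinary practice and not in themselves an error. No decision within this trial depends on the interaction results. All of that stands, and it confines the point to the confirmation label.

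Several stronger readings are tempting but not supported:

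- **That the two subsections contradict each other outright.** They do not. The multiplicity text places emphasis on estimates; it does not bar P values. There is tension, not a contradiction.
- **That 37% is simply the error rate.** It holds only for independent tests with no true interaction. Some modifiers plainly overlap, such as SOFA with shock and FiO2 with hypoxemic failure, so a range with its assumptions is the fair statement.
- **That ignoring the monthly block structure makes these figures worse.** All nine modifiers vary between patients within a block, so a shift shared by a block largely cancels from the interaction. In a linear simulation (nine blocks of 67, a modifier present in 40%, the plan's intra-cluster correlation of 0.01, no true effects, blocks ignored), the interaction test rejected about 5% of the time, while the group main-effect test rejected about 16%. Inflation appeared only when the modifier's own effect was assumed to vary between blocks, and the documents give no figure for that.
- **That a false finding would set eligibility or stratification in the later trial.** Section 2.0 says a large trial is needed and that feasibility data must come first. Nothing says that interaction results will feed its design.
- **That the 0.10 threshold must go too.** Its wording is already tentative, and removing it is a matter of preference.

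**Conclusion.** The concern holds in limited form. A rule that treats P<0.05 as confirming an interaction, applied to nine uncorrected tests in a trial powered only for a 3-day main effect, carries roughly a 28–37% chance of at least one false confirmation when no interaction exists. The top of the range assumes independence and the bottom a common correlation of 0.5; counting indication once gives 30%. Only stronger correlations than these bring the chance lower, and even at 0.9 it is nearly three times 5%.

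The figures assume one overall P value per modifier; separate P values for each pair of modes would mean more tests. The effect is on interpretation and reporting only. It deserves correction because the plan, followed as written, would allow a conclusion that its tests cannot carry.

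**What to change.** In the effect-modification subsection:

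1. Remove the statement that an interaction P value below 0.05 confirms an interaction.
2. Report each interaction estimate with its 95% confidence interval, adding the P value if wanted.
3. State that all nine analyses are exploratory and hypothesis-generating. This brings the subsection into line with the multiplicity text.
4. Only if a claim of confirmation is to be kept, tie it to a threshold corrected over the nine modifiers: Holm, or 0.05/9 = 0.0056.

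The tentative 0.10 wording may stay or go. The change needs no new data and no change to the design, models or sample size. The cost is that no interaction can be called confirmed from this pilot or, under item 4, only one that passes a much stricter threshold with low power to do so.

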- **The intervention is delivered by unit-level protocols.** Mechanical ventilator settings and titrations are performed by respiratory therapists using unit-level protocols. In this cluster-randomized trial, the entire unit will be assigned to the same mode of mechanical ventilation for each 1-month block. Obtaining informed consent from every eligible patient in the ICU prior to emergency tracheal intubation and initiation of mechanical ventilation would be impracticable.

Because the study involves minimal risk, the study would not adversely affect the welfare or privacy rights of the participant, and obtaining informed consent would be impracticable, we will request a waiver of informed consent. Numerous previous randomized trials comparing two standards of care for interventions such as emergency intubation and methods of respiratory support during critical illness have been completed with waiver of informed consent.^{39–47}

6.5 Randomization:

During each one-month block of the study, the ICU will be assigned to either volume control, pressure control, or adaptive pressure control. The order of the study group assignments will be generated by computerized randomization using permuted blocks of 3 to minimize the impact of seasonal variation. The last 3 days of each block will be a washout period during which the ICU will continue to use the assigned mode, but new patients will not be included in the primary analysis. The 3-day washout period will limit the number of patients who experience a ‘crossover’ from one assigned mode to another while receiving a mandatory mode of mechanical ventilation.

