7.6 Outcome Measures:**Primary Outcome:**

The primary outcome is ventilator-free days (VFDs) to day 28 after enrollment.

VFDs will be defined as the number of calendar days alive and free of invasive mechanical ventilation from the final receipt of invasive mechanical ventilation through 28 days after enrollment. Outcome ascertainment will cease at the time of hospital discharge or 28 days after enrollment, whichever occurs first. Receipt of invasive mechanical ventilation will be considered to end when patients undergo the final tracheal extubation or disconnection of the ventilator from a tracheostomy tube between enrollment (day 1) and day 28 after enrollment. Patients who die prior to discharge on or before day 28 will receive zero VFDs. Patients whose final receipt of invasive mechanical ventilation occurs on the day of enrollment and survive to day 28 will receive 27 VFDs. Patients who continue to receive invasive mechanical ventilation at day 28 will receive zero VFDs. Patients who are discharged from the hospital prior to day 28 and are receiving invasive mechanical ventilation at the time of discharge will receive zero VFDs. Patients who are removed from invasive mechanical ventilation and are discharged from the hospital without invasive mechanical ventilation prior to 28 days will be assumed to remain alive and

free of invasive mechanical ventilation between hospital discharge and day 28. For patients who are removed from invasive mechanical ventilation, return to invasive mechanical ventilation, and are subsequently removed again from invasive mechanical ventilation prior to day 28, VFDs will be counted from the final receipt of invasive mechanical ventilation prior to day 28.

Feasibility Outcomes

- Exposure to assigned study mode in first 3 days: proportion of time in the assigned mode while receiving invasive mechanical ventilation in the study ICU between enrollment and 72 hours after enrollment.
- Adherence to study mode in first 3 days: proportion of time in the assigned mode while receiving invasive mechanical ventilation in the study ICU with a mandatory mode between enrollment and 72 hours after enrollment (excluding time spent in spontaneous modes).
- Time from enrollment to initiation of assigned mode of mechanical ventilation
- Receipt of a "Mode Modification Sheet" completed by treating clinicians

Exploratory Efficacy and Safety Outcomes

- Median exhaled tidal volume (mL/kg predicted body weight (PBW)) on each study day

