10.0 Statistical Considerations

Sample size justification.

The purpose of this trial is to assess feasibility of a cluster-randomized, cluster-crossover design. To assess whether compliance can be maintained after cross-over events, we will need to observe two cross-over events to each mode while maintaining an equal number of treatment blocks for each mode. Doing so will require a total of 9 months. Based on the experience of a prior trial in the same ICU,⁷⁰ we anticipate an average of 75 patients on mechanical ventilation will be enrolled per month. In 9 months, we expect to enroll 675 patients, of whom 69 will be enrolled during washout periods and excluded from the primary analysis. The resulting 606 patients will be included in the primary analysis.

While the sample size was determined to demonstrate feasibility of the cluster-crossover design, we anticipate this pilot will be the largest randomized trial of ventilator modes to date, and as such, we plan to compare ventilator free days to day 28 (primary outcome) between groups. In a prior cluster-randomized cluster-crossover trial in the same ICU,⁷⁰ mechanically ventilated patients experienced a median of 22 VFDs [IQR 0-25 VFDs] and an intra-cluster intra-period correlation of 0.01. With 606 (202 in each group) patients in the primary analysis, a standard deviation in the primary outcome of VFDs of 11 days, and a two-sided alpha of 0.05, the MODE trial will have 80 percent statistical power to detect an absolute difference between groups in the sole primary clinical endpoint of Ventilator Free Days of 3 days.

Primary Analysis of the Primary Clinical Outcome

The sole pre-specified primary outcome of ventilator free days will be compared between the three trial groups in an intention-to-treat fashion among all patients enrolled in the trial except those admitted during one of the 3-day washout periods. To estimate the conditional effect of a group assignment on an individual patient given the values of the covariates for that patient, we will use a proportional odds model with independent covariates of group assignment (volume control, pressure control, or adaptive

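### Patients enrolled in washout periods are in no planned final between-mode comparison of the safety outcomes or in-hospital mortality

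*Combined protocol and SAP*

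**What the plan says.** Section 6.5 defines the washout: "The last 3 days of each block will be a washout period during which the ICU will continue to use the assigned mode". Patients who start ventilation in those days are enrolled and receive the assigned mode, but do not count in the primary analysis.

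Section 10.0 then sets three populations.

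- Primary analysis: the comparison is made "among all patients enrolled in the trial except those admitted during one of the 3-day washout periods". The sample size paragraph gives the numbers: "In 9 months, we expect to enroll 675 patients, of whom 69 will be enrolled during washout periods and excluded from the primary analysis". It continues: "The resulting 606 patients will be included in the primary analysis".
- Exploratory outcomes: "Each of the exploratory outcomes will be compared between groups in an intention-to-treat fashion in the primary analysis population".
- All-patient sensitivity analysis: "We will repeat the analyses of the primary outcome and feasibility outcomes among all patients enrolled in the trial", including those from the washout periods. No other outcome is named.

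Section 7.6 lists hypoxemia, severe acidemia, and pneumothorax or pneumomediastinum under "Exploratory Efficacy and Safety Outcomes", and in-hospital mortality under the exploratory clinical outcomes. The feasibility outcomes form a separate list.

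Two other places bear on the point. Section 9.4 treats primary and exploratory outcomes as clinical outcomes, not adverse events, unless someone judges the event related. Its reason is that death and organ dysfunction will be gathered and analyzed for every patient. The Interim Analysis paragraph has the DSMB compare three outcomes (pneumothorax or pneumomediastinum, hypoxemia, in-hospital mortality) across groups after three months, and does not state the population.

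**The concern.** Leaving washout patients out of the efficacy contrast is sensible, because many of them may spend only a short time in the assigned mode. Safety is a different question. These patients are enrolled under a requested waiver of consent, the trial sets their initial mode, and they are exposed to the intervention from the start of ventilation. Section 6.5 explains the washout by the wish to limit patients who cross from one assigned mode to another, so the plan itself expects them to be close to a block change. Because the ICU keeps using the assigned mode, the washout does not remove that exposure; it only removes the patients from the analysis.

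Section 9.4 raises the stakes. If a pneumothorax or hypoxemic episode in a washout patient is not judged related, it is not recorded as an adverse event. The protection offered in its place is analysis of the outcome in all patients. As Section 10.0 stands, the final between-mode analysis does not provide that for this group.

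**Working it through.** **1. Reproduce the plan's counts** (Section 10.0, sample size paragraph).
- Enrolled: 9 months × 75 per month = 675.
- Primary analysis: 675 − 69 = 606; 606 / 3 = 202 per mode.
- Washout: nine periods of 3 days are 27 days, and the time covariate runs to day 272. 675 × 27/272 = 67.0; with a 30-day month, 675 × 3/30 = 67.5. Both agree with the stated 69 to within about two patients, so 69 is used below.

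**2. Trace each outcome through the planned between-mode comparisons.**

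| Outcome | Final, primary population | Final, all-patient repeat | Three-month interim |
|---|---|---|---|
| Ventilator-free days (death = 0) | yes | yes | no |
| Feasibility outcomes | yes | yes | no |
| Pneumothorax or pneumomediastinum | yes | not named | yes, population unstated |
| Hypoxemia | yes | not named | yes, population unstated |
| In-hospital mortality | yes | not named | yes, population unstated |
| Severe acidemia | yes | not named | no |

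Washout patients are absent from the second column and present in the third. For the last four rows they have no final comparison.

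**3. Size of the group.** 69/675 = 10.2% of enrolled patients; 69/3 = 23 per mode.

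**4. What the interim could recover.** Three months × 75 = 225 enrolled, of whom 69 × 3/9 = 23 are washout patients. The interim would cover 225 if they are kept and 202 if they are dropped. At least 69 − 23 = 46 washout patients are therefore in no planned between-mode comparison of the three interim outcomes. For severe acidemia it is all 69.

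**5. Events involved.** Section 2.0 gives in-hospital mortality of 25–35%: 69 × 0.25 = 17 to 69 × 0.35 = 24 deaths. The documents give no rates for the other outcomes. At assumed rates of 2%, 5% and 10%, 69 patients would contribute 1.4, 3.5 and 6.9 events.

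**6. Precision gained by adding them.** Treating patients as independent, the ratio of standard errors is √(606/675) = 0.948, about 5% smaller. If the correlation of 0.01 that Section 10.0 quotes from the prior trial also applied to these outcomes, the design effect would be 1 + (606/9 − 1) × 0.01 = 1.663 before and 1 + (75 − 1) × 0.01 = 1.74 after. The ratio would be √[(202/1.663)/(225/1.74)] = 0.969, about 3% smaller.

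**7. Patients still ventilated at a block change (illustration only).** Assume exponential ventilation time with mean m days and uniform enrollment over a 30-day block. The probability of still being ventilated at block end is (m/3)(1 − e^(−3/m)) for washout patients and (m/27)(e^(−3/m) − e^(−30/m)) for primary-analysis patients. For m = 4, 6 and 8 this gives 0.704, 0.787 and 0.834 against 0.070, 0.133 and 0.197. Nine blocks have only eight changes, so the counts are 69 × 8/9 × 0.704 to 0.834 = 43 to 51 washout patients, and 606 × 8/9 × 0.070 to 0.197 = 38 to 106 primary-analysis patients.

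**The case against.** The strongest reply is that this is a pilot, the outcomes are exploratory and reported as estimates with intervals, and the primary analysis is unaffected. Restricting the main safety comparison to the primary population is also defensible. Pooling washout patients by assigned mode would credit some of the next mode's exposure to the first mode, which may dilute a real difference. Washout patients are not unmonitored either: daily adverse-event evaluation (Section 9.2) covers patients whose mode the trial controls, and the DSMB reviews trial data (Section 13.0). All of this stands. It supports keeping the present comparison as the main one, but it does not explain why the all-patient repeat stops short of safety. Adverse-event evaluation does not fill the gap, because Section 9.4 exempts these events unless judged related and no between-group comparison of adverse events is planned.

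A reader might infer two stronger claims that the documents do not support.

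- *That washout patients are in no between-mode safety comparison at all.* The interim paragraph states no washout exclusion, so about 23 of them may be in it, and deaths before discharge by day 28 enter the all-patient repeat of ventilator-free days as zeros. That composite says nothing about pneumothorax, hypoxemia or acidemia.
- *That a third to a half of all switched patients are lost to safety analysis.* The illustration in step 7 would put washout patients at 33–53% of those ventilated across a block change. But the ventilation-time distribution is assumed, and it counts patients still ventilated, not patients switched. Some will be on spontaneous modes, transferred out or under a Mode Modification Sheet. Section 7.1 ends protocol control of the mode at the end of the block, and the documents give no switching rate.

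Nor would an all-patient comparison by assigned mode isolate harm from a block change. That is a reason to tabulate washout patients separately as well as to pool them.

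**Conclusion.** The point holds as a gap in safety accounting, not as a flaw in the primary analysis. On the current text, the expected 69 of 675 patients are outside every planned final between-mode comparison of hypoxemia, severe acidemia, pneumothorax or pneumomediastinum, and in-hospital mortality as an outcome in its own right. This conflicts with the rationale in Section 9.4 for not recording such events as adverse events.

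The counts rest on the plan's own enrollment forecast. The upper limit of 23 at the interim assumes washout enrollment is spread evenly over the nine blocks. The gain in precision is small, about 5% under independence and less with within-period correlation, so the case for change rests on completeness. Any figure for switched patients is an assumption and is not needed for the conclusion.

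**What to change.** Four changes to Section 10.0:

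1. In the sensitivity analyses, extend the all-patient repeat to the exploratory safety outcomes and in-hospital mortality. Suggested text: *The analyses of the primary, feasibility and exploratory safety outcomes and of in-hospital mortality will be repeated in all enrolled patients, with washout enrollees included.*
2. Keep the comparison in the primary analysis population as the main one for these outcomes.
3. Add a table of event counts and denominators for washout patients alone, by assigned mode. It would be descriptive, since about 23 patients per mode will not support a formal test.
4. In the Interim Analysis paragraph, state that the safety data given to the DSMB cover all enrolled patients by assigned mode, with washout patients also shown separately.

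The cost is a few sentences, one more run of the analysis code and one table. The outcomes come from the same electronic extraction, the all-patient dataset is already planned, and the primary comparison does not change. The final analysis would then match what Section 9.4 promises.
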